PFS	Progression-Free Survival
PR	Partial Response
QW, Q2W, Q3W, Q8W, Q9W	Every Week, Every 2 Weeks, Every 3 Weeks, Every 8 Weeks, Every 9 Weeks
RAS mCRC	Extended RAS mutated CRC (Extended RAS= KRAS and NRAS)
RBC	Red Blood Cell
RECIST	Response Evaluation Criteria In Solid Tumors
iRECIST	Immune Response Evaluation Criteria In Solid Tumors
ROC	Receiver Operator Characteristic
SAE	Serious Adverse Event
SAS	Statistical Analysis System
SD	Stable Disease
SE	Safety Evaluable
SUSAR	Suspect Unexpected Serious Adverse Reaction
TMF	Trial Master File
TMZ	Temozolomide

ULN	Upper Limit of Normal
WBC	White Blood Count / White Blood Cells
WKS	Weeks
WT	Wild Type

2.0 SUMMARY

Abbreviated Title	THE ARETHUSA TRIAL
Trial Phase	2
Clinical Indication	Metastatic colorectal cancer
Trial Type	Interventional
Type of control	NA
Route of administration	Intravenous Pembrolizumab and oral Temozolomide
Trial Blinding	NA
Treatment Groups	TMZ priming followed by Pembrolizumab
Number of trial participants	54 in TRIAL Phase 67 PRIMING Phase 670 SCREENING Phase
Estimated enrollment period	24 months
Estimated duration of trial	36 months (40 months to final report)
Duration of Participation	36 months + Follow Up
Estimated average length of treatment per patient	6 months (Pembrolizumab); 3 months (Temozolomide)

3.0 SYNOPSIS

Protocol Number	IFOM-CPT002/2018/PO001
Title	PEMBROLIZUMAB IN MMR-PROFICIENT METASTATIC COLORECTAL CANCER PHARMACOLOGICALLY PRIMED TO TRIGGER DYNAMIC HYPERMUTATION STATUS
Brief title	THE ARETHUSA TRIAL
Sponsor	IFOM - Istituto FIRC di Oncologia Molecolare
Clinical Phase	Phase II
Study Rationale	
ARETHUSA has been designed on the basis of four translational findings, namely that: i) pembrolizumab is active only in MMR deficient mCRC patients; ii) the DNA alkylator temozolomide is active only in mCRC patients whose tumor harbours a silenced O-6-methylguanine-DNA methyltransferase (MGMT), a DNA repair enzyme that removes alkylated adducts from the DNA. MGMT is silenced by gene promoter hypermethylation, a favourable context of susceptibility to DNA damage (Amatu et al., 2016; Esteller and Herman, 2004); iii) in the tumor specimens of mCRC patients with MMR proficient tumors collected at treatment progression we observed that resistance to TMZ correlated with inactivation of MMR and increased mutational loads (Germano et al., 2017) iv) TMZ can cause inactivation of DNA repair, increased mutational burden and effective immune surveillance in preclinical models, de facto turning a MMR-P tumors into a ‘MMR-D like’ (Germano et al., 2017).
 
Moreover, mutational load has been correlated with response to immune checkpoint blockade. In particular clinical evidence, mostly derived from melanoma patients treated with ipilimumab, suggests that the mutational burden associated with clinical benefit is between 10 and 20 mutations per MB (Lauss et al., 2017; Snyder et al., 2014; Van Allen et al., 2015). Indeed a recent study (Panda et al., 2017) in 224 colorectal cancer shows that 100% of 193 cases with < 20 mutations were MMR proficient and that 100% of 31 cases with > 20 mutations were either MMR-deficient (n 28) or POLE mutated (n 3). Thus, an absolute mutational load cutoff of 20 mutations per MB was able, in CRC patients, to detect with digital sensitivity and specificity the subset of patients most likely to achieve a clinical response from immunotherapy.
 
Collectively these results suggest that an increase in mutational load (and the ensuing neo-antigen burden) induced by TMZ treatment, might sensitize to immune checkpoint blockade, and drive the rationale of the ARETHUSA trial. A 20

	mutations/MB has been defined as the absolute post-temozolomide cut-off value for patient eligibility on the basis of the studies reported above.
Primary Objective	To assess the objective response rate of pembrolizumab in metastatic MMR proficient, extended RAS mutated CRC patients who have failed standard therapies, with MGMT-negative tumors treated with TMZ, given with the intent of increasing the mutational load of their tumors (cohort P).
Secondary Objective(s)	
 • To assess the objective response rate in MMR deficient patients (cohort D) identified during the MMR screening. • To assess the Progression Free Survival (PFS) and Overall Survival (OS) both P and D cohorts patients. • To assess the safety and tolerability of pembrolizumab after TMZ-priming therapy (cohort P). • To assess the safety and tolerability of pembrolizumab (cohort D).
Translational Objective(s)	
 • To validate the assessment of mutational load in plasma using the tissue mutational load as ‘gold’ standard. • To assess the relationship between selected immune biomarkers in archival and/or fresh tumor tissue and blood with response to pembrolizumab. • To compare these immunomarkers profiles prior and after TMZ in cohort P patients, and prior and after pembrolizumab treatment in all patients (cohort D and P). • To assess the relationship of RAS status in MMR deficient patients (cohort D) with response to Pembrolizumab.
Primary Endpoint	Objective response rate (ORR) to pembrolizumab in cohort P according to RECIST (as specified in table 9.1.3).
Secondary Endpoint(s)	
 • ORR to pembrolizumab in cohort D according to RECIST (as specified in table 9.1.3). • PFS and OS in both cohorts P and D. • Safety and tolerability according to CTCAE version 4.03.
Translational endpoint(s)	
 • Validation of tumor mutational load assessment in plasma. • Expression of immune markers and their correlation with response to temozolomide and pembrolizumab. • ORR to pembrolizumab in RAS and non-RAS mutant stratified cohort D according to RECIST.
Trial Design	2-cohort, open label, transformative, precision medicine, phase II trial in extended RAS-mutated MMR-Proficient metastatic CRC (RAS mCRC) and unselected MMR-Deficient mCRC patients refractory to standard treatments. Extended RAS

	
mutations include KRAS and NRAS mutations. The trial consists of 3 different phases:
 
Screening Phase: MMR-Deficient (MMR-D) patients proceed directly to TRIAL Phase (cohort D) to be treated with pembrolizumab. RAS mutant MMR-Proficient (MMR-P) patients, instead, are further tested for O6-methylguanine–DNA methyltransferase gene expression (MGMT) status in tissue (MGMT protein IHC and MGMT promoter methylation). MGMT IHC negative and promoter methylated patients will proceed to PRIMING phase.
 
Priming Phase: MMR-P patients showing negative MGMT protein and high levels of MGMT promoter methylation in tissues will receive TMZ therapy until progression. Two tumor biopsies will be taken prior to starting therapy and at progression to determine the mutational load. Patients with a mutational load < 20 mutations/megabase will go off-study. Patients with a mutational load ≥ 20 mutations/megabase, will proceed to trial phase no longer than week 5 post TMZ-ML.
 
Trial Phase: Eligible patients, i.e. MMRD patients (cohort D) and patients with a TMZ-ML ≥ 20 mutations per megabase at TMZ-ML (cohort P), will be treated with pembrolizumab 200 mg administered as an intravenous infusion over 30 minutes every 3 weeks until disease progression, unacceptable toxicity, or up to 24 months in patients without disease progression.

Inclusion Criteria	
Patient selection criteria are progressively restrictive according to the 3-step selection strategy of the trial and are reported separately for each phase.
 
SCREENING Phase
 
 1. Histologically confirmed diagnosis of metastatic colorectal cancer. 2. Documented RAS extended mutations in the archival sample (cohort P only). 3. ECOG performance status 0-1. 4. SCREENING phase informed consent signed. 5. Understanding and accepting the need for undergoing two tumor biopsies if eligible for PRIMING Phase. 6. Age ≥ 18 years. 7. Availability of all diagnostic FFPE blocks (primary tumor and or metastases), or at least 20 slides (primary tumor and/or metastases). Formalin-fixed, paraffin embedded (FFPE) tissue blocks are preferred to slides.

	
8. Normal organ functions.
 
PRIMING Phase
 
 1. Fulfilment of all the SCREENING inclusion criteria; 2. PRIMING informed consent signed; 3. Confirming the willingness to undergo two tumor biopsies, 4. Acceptance that, if the mutational load determination is unfeasible for technical reasons (not enough tissue, substandard test performance, etc.), access to TRIAL phase will not be possible. 5. Imaging documented failure of previous standard CRC therapies including fluoropyrimidine, oxaliplatin, irinotecan plus or minus antiangiogenics agents (Bevacizumab, Aflibercept, Regorafenib, others). 6. At least one measurable tumor lesion as per RECIST v1.1. Lesions in previously irradiated areas or those that have received other loco-regional therapies (i.e. percutaneous ablation) should not be considered measurable unless there is clear documented evidence of progression of the lesion since therapy. Imaging must be performed maximum within 28 days prior to enrolment. 7. ECOG performance status 0 or 1; 8. Following results in the SCREENING Phase tests: 
 • Proficient MMR status assessed by IHC or MSI-Low status defined by PCR (Bethesda panel); • Negative score for the MGMT protein expression IHC test; • Positive score for the MGMT promoter methylation performed on Tissue. 9. Women with childbearing potential should complete a pregnancy test and be willing to use highly effective contraceptive methods. 10. Normal organ functions. 
TRIAL Phase
 
 1. Fulfilment of all the SCREENING inclusion criteria and Deficient MMR status (IHC) or MSI-High status (PCR) (cohort D only). 2. Fulfilment of all the SCREENING and PRIMING inclusion criteria (cohort P only). 3. TRIAL Phase informed consent signed (both cohorts). 4. Imaging documented PD to TMZ (cohort P only). 5. A mutational load value ≥ 20 mutations/MB at TMZ-ML assay (cohort P only).
--	---

	
6. Imaging documented failure of previous standard CRC therapies including fluoropyrimidine, oxaliplatin, irinotecan plus or minus targeted agents (Bevacizumab, Aflibercept, Regorafenib, Cetuximab, Panitumumab, others) (cohort D only).
 
7. At least one measurable tumor lesion as per RECIST v1.1. Lesions in previously irradiated areas or those that have received other loco-regional therapies (i.e. percutaneous ablation) should not be considered measurable unless there is clear documented evidence of progression of the lesion since therapy. Imaging must be performed maximum within 28 days prior to enrolment (both cohorts).
 
8. Woman with childbearing potential should complete a pregnancy test and be willing to use highly effective contraceptive methods (both cohorts).
 
9. Normal organ functions. Blood specimens must be collected within 10 days prior to the start of study treatment (both cohorts).
 
See exclusion criteria in the protocol
					

Treatments
	
Drug
	
Dose/Potency
	
Dose Frequency
	
Route of Administration
	
Regimen/Treatment Period
	
Use

	
Temozolomide
	
150 or 200 or 100 mg/ (7.3.1.2)
	
Q4W
	
P.O.
	
Days 1-5 every 28 days (PRIMING Phase)
	
Experimental

	
Pembrolizumab
	
200 mg
	
Q3W
	
IV infusion
	
Day 1 of each 3 week cycle (TRIAL Phase)
	
Experimental

Sample Size
	
A two-stage Green-Dahlberg design has been used to calculate the sample size for the P-cohort under the following assumptions:
 
 • The null hypothesis that the true (H_0) response rate is 10% (not considered clinically compelling) will be tested against a one-sided alternative (H_1). • In the first stage, 10 patients will be accrued. If no responses are observed, the study will be stopped. Otherwise, 10 additional patients will be accrued for a total of 20. • The null hypothesis will be rejected if 5 or more responses are observed in 20 patients. • This design yields a type I error rate of 0.05, and power of 90% when the true response rate is 40%. • In order to recruit 20 patients in the P-cohort the number of MMR unselected patients to be pre-screened for MMR status MGMT promoter 					

methylation and the number of MGMT-PM+ to be primed with TMZ are reported in the Table below		
Number of Patients to be:	N	Expected Percent
RAS mutant MMR proficient cases to be screened	670	A
expected MGMT IHC negative	335	B = 50% of A
expected promoter methylated in tissue	67	C = 20% of B and 10% of A
expected with increase of mutational load ≥ 20 mutations/Mb (PRIMING Phase)	20	D= 30% of C

For cohort D a precise sample size has NOT been calculated since the ORR in deficient patients is a secondary objective of the trial. We will enroll up to 34 MMR-D cases according to an estimated prevalence of 4-5%. These patients will constitute the D-cohort. We expect a response rate between 40% (95% C.I .18-.71) and 33% (95% C.I .21-.46) as reported by Le et al (2015 & 2019) with 11-14 responses accordingly.
		

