7.1.3 Entry Criteria for TRIAL Phase

1. Fulfilment of all the SCREENING inclusion criteria and deficient MMR status (IHC) or MSI-High status (PCR) (cohort D only).
2. Fulfilment of all the SCREENING and PRIMING inclusion criteria (cohort P only).
3. TRIAL Phase informed consent signed (both cohorts).
4. Imaging documented PD to TMZ (cohort P only).
5. A mutational load value ≥ 20 mutations/MB at TMZ-ML assay (cohort P only).
6. Imaging documented failure of previous standard CRC therapies including fluoropyrimidine, oxaliplatin, irinotecan plus or minus targeted agents (Bevacizumab, Aflibercept, Regorafenib, Cetuximab, Panitumumab, others) (cohort D only).
7. At least one measurable tumor lesion as per RECIST v1.1. Lesions in previously irradiated areas or those that have received other loco-regional therapies (i.e. percutaneous ablation) should not be considered measurable unless there is clear documented evidence of progression of the lesion since therapy. Imaging must be performed maximum within 28 days prior to enrolment (both cohorts).
8. Women with childbearing potential should complete a pregnancy test and be willing to use highly effective contraceptive methods (both cohorts).
9. Normal organ functions as defined in the Table 7.1.4 below. Blood specimens must be collected within 10 days prior to the start of study treatment.

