20. Is pregnant or breastfeeding, or expecting to conceive or father children within the projected duration of the study, starting with the screening visit through 120 days after the last dose of trial treatment.

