7.2.1.2 Contraception

ICH M3 guidance requires precautions to be taken to minimize risk to fetus or embryo when including women of childbearing potential in clinical studies.

Temozolomide and Pembrolizumab may have adverse effects on a fetus in utero. Refer to Appendix 3 for approved methods of contraception.

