7.2.2 Pregnancy

If a participant inadvertently becomes pregnant while on treatment with Temozolomide or pembrolizumab, the participant will be immediately discontinued from study treatment. The site will contact the participant at least monthly and document the participant's status until the pregnancy has been completed or terminated. The outcome of the pregnancy will be reported to delegated pharmacovigilance and to Merck Global Safety according to timelines as defined in section 9.2.3 if the outcome is a serious adverse experience (e.g., death, abortion, congenital anomaly, or other disabling or life-threatening complication to the mother or newborn). The study Investigator will make every effort to obtain permission to follow the outcome of the pregnancy and report the condition of the fetus or newborn to Merck. If a male participant impregnates his female partner, the study personnel at the site must be informed immediately and the pregnancy must be reported to delegated pharmacovigilance and to Merck Global Safety followed as described in section 9.2.3.

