9.2.2 Reporting of Adverse Events

AEs will be collected from the time the first dose of study medication (either pembrolizumab or temozolomide) is administered until 30 days following discontinuation of study treatment. SAEs will be collected over the same time period as stated above for AEs of temozolomide, or up to 90 days for pembrolizumab. In addition, any SAE assessed as related to study participation, study medication or concomitant medication must be recorded from the time a subject consents to participate in the study up to and including any follow-up contact. After discontinuation of study medication, the investigator will monitor all AEs/SAEs that are ongoing until resolution or stabilization of the event or until the subject is lost to follow-up.

Reporting criteria for AEs/SAEs:

- All AEs, SAEs and other reportable safety events that occur after the consent form is signed but before planned treatment initiation must be reported by the investigator if the event cause the participant to be excluded from the study.
- All AEs must be reported by the investigator from the time of treatment allocation through 30 days following cessation of study treatment.
- SAEs regarding pembrolizumab must be reported by the investigator from the time of treatment allocation through 90 days (pembrolizumab) or 30 days (temozolomide) following cessation of study treatment, or 30 days following cessation of study treatment if the participant initiates new anticancer therapy, whichever is earlier.
- All pregnancies must be reported by the investigator from the time of treatment allocation through 120 days (pembrolizumab) or 90 days (temozolomide) following cessation of study treatment, or 30 days following cessation of study treatment if the participant initiates new anticancer therapy, whichever is earlier.

- Any SAE brought to the attention of an investigator at any time outside of the time period specified above must be reported immediately by the investigator if the event is considered to be study drug-related.
- A death on study requires reporting regardless of causality and attribution to treatment or other cause must be provided. Death due to disease progression is not to be reported as an AE. Deaths that occur beyond 30 days after the end of study drug administration/initiation of an alternate therapy, do not qualify as SAEs.

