Appendix 3: Contraception Requirements

Female Participants:

Female participants of childbearing potential are eligible to participate if they agree to use one of the contraception methods described in Table A3 consistently and correctly during the protocol-defined time frame in section 8.0 and 9.0.

Table A3: Contraceptive Methods

Acceptable Contraceptive Methods
Failure rate of >1% per year when used consistently and correctly.

 ● Male or female condom with or without spermicide ● Cervical cap, diaphragm or sponge with spermicide

Highly Effective Contraceptive Methods That Are User Dependent ^a
 
Failure rate of <1% per year when used consistently and correctly.
 
 ● Combined (estrogen- and progestogen- containing) hormonal contraception ^b 
 ○ Oral ○ Intravaginal ○ Transdermal ○ Injectable ● Progestogen-only hormonal contraception ^b 
 ○ Oral ○ Injectable

Highly Effective Methods That Have Low User Dependency
 
Failure rate of <1% per year when used consistently and correctly.
 
 ● Progestogen- only contraceptive implant ^{b, c} ● Intrauterine hormone-releasing system (IUS) ^b ● Intrauterine device (IUD) ● Bilateral tubal occlusion

 ● Vasectomized partner A vasectomized partner is a highly effective contraception method provided that the partner is the sole male sexual partner of the WOCBP and the absence of sperm has been confirmed. If not, an additional highly effective method of contraception should be used. ● Sexual abstinence Sexual abstinence is considered a highly effective method only if defined as refraining from heterosexual intercourse during the entire period of risk associated with the study treatment. The reliability of sexual abstinence needs to be evaluated in relation to the duration of the study and the preferred and usual lifestyle of the participant.)

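### No contraception requirement for male participants in the PRIMING or TRIAL criteria, or in Appendix 3

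*Combined protocol and SAP*

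**What the plan says.** PRIMING criterion 9 reads: "Women with childbearing potential should complete a pregnancy test and be willing to use highly effective contraceptive methods". It appears in the Synopsis and again in section 7.1.2. TRIAL criterion 8, in the Synopsis and section 7.1.3, says the same for both cohorts. Neither mentions men.

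Section 7.2.1.2 states the risk and points to the methods: "Temozolomide and Pembrolizumab may have adverse effects on a fetus in utero. Refer to Appendix 3 for approved methods of contraception". Appendix 3 then opens under a heading for female participants: "Female participants of childbearing potential are eligible to participate if they agree to use one of the contraception methods described in Table A3". It has no counterpart for men. The male condom and the vasectomized partner do appear in Table A3, but as methods for the female participant.

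Three other places bear on men:

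- Exclusion criterion 20 excludes anyone "expecting to conceive or father children within the projected duration of the study, starting with the screening visit through 120 days after the last dose".
- Section 7.2.2 sets a reporting duty: "If a male participant impregnates his female partner, the study personnel at the site must be informed immediately".
- Section 9.2.2 sets the reporting window: "All pregnancies must be reported by the investigator from the time of treatment allocation through 120 days (pembrolizumab) or 90 days (temozolomide) following cessation". The window is shortened if new anticancer therapy is started.

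**The concern.** The plan treats conception by a male participant as something to avoid, since it excludes men who expect to father a child and wants partner pregnancies reported. Yet it sets no rule that would prevent an unplanned one. This is an omission rather than a contradiction.

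What is at stake is the safety of partners and offspring. Temozolomide is described in the rationale as a DNA alkylator and is given here in order to raise the mutational load. Exposure can be long: temozolomide runs until progression, and pembrolizumab for up to 24 months with a possible second course of 17 cycles. No endpoint, error rate or sample size depends on the point.

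**Working it through.** The check is mainly a reading of every provision on contraception, pregnancy and fathering children, asking what each requires of a man and when.

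| Provision | Women of childbearing potential | Men |
|---|---|---|
| PRIMING criterion 9 (Synopsis, 7.1.2) | Pregnancy test and highly effective contraception | Nothing |
| TRIAL criterion 8 (Synopsis, 7.1.3) | The same | Nothing |
| Exclusion 1 (7.2) | Negative serum test within 72 hours before allocation | Not applicable |
| Exclusion 20 (7.2) | Not pregnant, breastfeeding or expecting to conceive | Not expecting to father a child, through 120 days after the last dose |
| 7.2.1.2 and Appendix 3 | Table of methods | No heading, method or period |
| 7.2.2, 7.7 | Stop treatment on pregnancy; follow the outcome | Report a partner's pregnancy |
| 9.2.2 | Report for 120 days (pembrolizumab) or 90 days (temozolomide) | Same windows; the sentence covers all pregnancies |

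Now take a man who has a partner of childbearing potential, does not plan a child and uses no contraception.

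1. PRIMING criterion 9 and TRIAL criterion 8 do not apply to him.
2. Exclusion 20 asks what he expects. He expects no child, so he is not excluded.
3. Appendix 3 sets him no condition.
4. Section 7.2.2 takes effect only once his partner is pregnant.

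He is therefore eligible and is treated, with the plan followed exactly. Appendix 3 reads continuously from the table into its notes, so a male section is unlikely to have been lost in text extraction.

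**How many people could be concerned.** The inputs are the planned numbers in the Summary (section 2.0) and section 10.2: 67 in PRIMING, 54 in TRIAL, 20 in cohort P and up to 34 in cohort D.

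- TRIAL total: 20 + 34 = 54, as stated in the plan.
- Distinct treated patients, since the 20 in cohort P come from the 67: 67 + 54 − 20 = 67 + 34 = 101.
- Temozolomide only: 67 − 20 = 47. These patients never reach the TRIAL criteria, so a rule placed only there would miss them.
- Men, at an assumed share of 40–60% (not in the documents): 0.40 × 101 = 40.4 and 0.60 × 101 = 60.6, or about 40–61.

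The last range is an upper bound on those concerned for the planned 101, because only men with a partner of childbearing potential count and that share is unknown. The 101 is itself a planning figure, since section 7.8 allows replacements in both phases.

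**The case against.** The strongest reply is that the need for the rule is not shown from the documents. The one risk sentence, in section 7.2.1.2, concerns a fetus in utero and follows a sentence about including women. No visible text describes a risk carried through the father, and none separates the two drugs on this point, although cohort D receives pembrolizumab only. Male advice may well sit elsewhere: section 7.3.1.5 refers to the temozolomide SmPC for warnings, section 6.1.3 refers to the Investigator's Brochure, and the consent forms were not available. Exclusion 20 also gives real cover. It names fathering, runs to 120 days after the last dose, and under the flow chart in section 8.0 is reviewed at screening and again at the first cycle of each drug.

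Much of this is fair as a limit on the claim. The finding is about what the visible protocol requires, and it cannot exclude advice in other documents. The repeated reviews do make exclusion 20 more than a single question, but each asks about the same expectation and none creates a duty during treatment. A pointer to a product label is not a condition that a participant agrees to, and for women the protocol does not rely on one. Section 9.1.1.1 says that the conditions in each consent form are defined by the eligibility criteria in 7.1 and 7.2, so a duty missing from those sections is not one the protocol requires consent to carry. What remains uncovered is unintended conception, which is narrower than having no provision for men at all but is the case a contraception rule exists for.

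A further objection also stands. Appendix 3 sends the reader to sections 8.0 and 9.0 for the women's period, and those sections give reporting windows but no duration for contraception. An explicit period for men alone would leave the women's rule the vaguer of the two.

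**Conclusion.** The concern holds. The protocol sets no contraception requirement for male participants in either treatment phase. Exclusion 20 and section 7.2.2 soften the gap without closing it. On the planned numbers it applies to the men among 101 treated patients, 47 of whom are expected to receive temozolomide only. The estimate of about 40–61 men rests on an assumed 40–60% share and overstates those concerned, because not all have a partner of childbearing potential.

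Two limits remain: the visible text states no risk through the father, and male advice in the SmPC, the Brochure or the consent forms cannot be ruled out. The point should be corrected for partner and offspring safety, and it does not affect the validity of the primary analysis.

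**What to change.** Add to PRIMING criterion 9 and TRIAL criterion 8, in the Synopsis and in sections 7.1.2 and 7.1.3:

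*Male participants with a partner of childbearing potential must agree to use contraception from the first dose through at least 120 days after the last dose of trial treatment.*

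Add a paragraph for male participants to Appendix 3 giving the same period and listing the accepted methods. Put the same sentence in the PRIMING and TRIAL consent texts if it is not already there. The 120 days is the period in exclusion 20 and covers both reporting windows in section 9.2.2 (120 and 90 days). Check it against the temozolomide SmPC and the Investigator's Brochure, and use the longer period if either asks for one. It would be sensible to state the women's period in Appendix 3 in the same amendment.

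The cost is a short wording amendment: one sentence in two criteria, each stated twice, one appendix paragraph and matching consent text. It may exclude an occasional man unwilling to use contraception.
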